9.3.2 Sensitivity Analyses

The primary analysis will be repeated for the subjects in the PP analysis set as sensitivity analysis, as well as in the ITT analysis set if the ITT analysis set differs from the mITT analysis set. The outcomes of these analyses are considered supportive.

The primary analyses described above will be repeated restricted to subjects with oocytes retrieved and to subjects undergoing blastocyst transfer, as applicable.

Missing data for the primary endpoint is expected to be limited due to the trial design, but may occur if the subject is lost to follow-up before ongoing pregnancy is assessed. If one or more such subjects have a positive pregnancy test result (β hCG test, clinical pregnancy or vital pregnancy) prior to loss to follow-up, the impact of imputing the ongoing pregnancy will be investigated in a sensitivity analysis.

It is also possible that a subject without pregnancy assessments following a transfer has her birth/miscarriage/elective termination outcome available at a later time. The information may be evaluated to help determine the ongoing pregnancy status in the sensitivity analysis on a case-by-case basis.

In order to assess the impact, if any, of the COVID-19 pandemic on the primary endpoint, additional sensitivity analyses are planned which will assess both the timing of the COVID-19 pandemic trial hold and the imputation method applied to missing data that arises due to the pandemic. The primary endpoint analysis is based on cryopreserved cycles initiated within 12 calendar months from the date of randomization (subsequently referred to as 12 calendar months). However, for a subset of subjects, part of their 12 calendar months will have been lost due to the COVID-19 pandemic trial hold. These subjects will be allowed to initiate cryopreserved cycles within 12 months of active study days (subsequently referred to as 12 study months). Because the last randomization occurred on 17 September 2019 and the trial hold began subsequent to the issuing of Protocol Amendment 01 on 19 March 2020, the first COVID-19 pandemic sensitivity analysis will repeat the same methodology as the primary endpoint analysis (i.e.; same analysis set, same inference method, and same imputation method), but will instead use the cumulative ongoing pregnancy rate from cycles initiated within the

first six calendar months following randomization. In this manner, all subjects can be evaluated using an equivalent time period. The second COVID-19 pandemic sensitivity analysis will again repeat the same methodology as the primary endpoint analysis, but with ongoing pregnancies observed within 12 study months. The third COVID-19 pandemic sensitivity analysis will, like the primary endpoint analysis, use data from all cycles initiated within 12 calendar months, but will apply a different imputation method for endpoint data that are missing due to the COVID-19 pandemic. The method of multiple imputation, as described in Section 9.2.2, will be applied to those endpoints that are missing specifically due to the pandemic.

Subgroup Displays

The primary endpoint will also be displayed by the following subgroups:

- Primary reason for infertility (unexplained infertility, tubal infertility, male factor, endometriosis stage I/II, other)
- Method of insemination (IVF, ICSI, IVF/ICSI)
- Age (35-37, 38-40, 41-42 years; ≤ median, > median)
- Body weight (≤ 75 , >75 kg; \leq median, > median)
- AMH on stimulation day 1 (<7.5, 7.5-<15, 15-<25, ≥25 pmol/L; ≤ median, > median)
- Center

For each subgroup factor, descriptive statistics for the cumulative ongoing pregnancy rate will be presented by subgroup level and treatment group. These subgroup displays will be prepared for the mITT and PP analysis sets.

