9.3 Primary Endpoint

The primary endpoint will be determined as soon as the subject has achieved an ongoing pregnancy, or when all cryopreserved blastocysts have been exhausted, or after assessment of ongoing pregnancy status in cryopreserved cycles initiated within 12 months from the start of controlled ovarian stimulation.

The superiority hypotheses to be tested for the primary endpoint are:

H₀: $\pi_{\text{FE 999049}} - \pi_{\text{Placebo}} \leq 0$ against the alternative H_A: $\pi_{\text{FE 999049}} - \pi_{\text{Placebo}} > 0$,

where $\pi_{FE 999049}$ and $\pi_{Placebo}$ denote the cumulative ongoing pregnancy rate after the fresh cycle and cryopreserved cycles in subjects aged 35-42 years treated with FE 999049 or placebo, respectively.

Ferring Pharmaceuticals

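### SAP 9.3.2 words the second COVID-19 sensitivity analysis by when a pregnancy is observed, not when its cycle was initiated; read literally, it omits pregnancies from late cycles that the primary counts

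*SAP*

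**What the plan says.** SAP 9.3 settles the primary endpoint at the latest "after assessment of ongoing pregnancy status in cryopreserved cycles initiated within 12 months from the start of controlled ovarian stimulation". Section 9.3.2 restates the rule: "The primary endpoint analysis is based on cryopreserved cycles initiated within 12 calendar months from the date of randomization". In both places the window governs when a cycle starts. The confirming scan may fall later.

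Section 9.3.2 then notes that "for a subset of subjects, part of their 12 calendar months will have been lost due to the COVID-19 pandemic trial hold", and gives the remedy: "These subjects will be allowed to initiate cryopreserved cycles within 12 months of active study days (subsequently referred to as 12 study months". So the term 12 study months enters the SAP as an initiation period.

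Three COVID-19 sensitivity analyses follow:

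- Analysis 1 counts cycles initiated in the first six calendar months after randomization.
- Analysis 2 is said to follow the primary in method, with one qualifying clause that sets its counting rule: "but with ongoing pregnancies observed within 12 study months".
- Analysis 3 will "use data from all cycles initiated within 12 calendar months", with multiple imputation for outcomes missing because of the pandemic.

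The multiple-imputation rule in SAP 9.2.2 also works by initiation date. SAP 11.1.1 says the COVID-19 analyses will be repeated for cumulative live birth, and does not restate the window.

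**The concern.** Analysis 2 is the only one of these that ties its window to observation. The ongoing-pregnancy scan comes many weeks after a cryopreserved cycle begins. A pregnancy from a cycle started late in the window therefore counts in the primary but, on the literal wording, not in analysis 2. All treated women stay in the denominator, so a pregnancy that is not counted becomes a failure.

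Analysis 2 exists to give back time lost to the hold. If a programmer applies the literal rule, it takes time away from some women instead. The comparison with the primary would then mix two things: the restored time and a changed counting rule. The second could be read as a pandemic effect.

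**Working it through.** **The plan's own figures.** The documents give no figure for the lag between initiation and confirmation. The nearest stated figure is power of at least 99% for 30% against 3% with 500:50 (SAP 3.2). It reproduces: the rule in SAP 9.3.1 (one-sided Fisher test if fewer than five placebo pregnancies, otherwise the Wald interval) has exact power above 99.9%, with Fisher at 0.05 or 0.025.

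**Lag from initiation to the ongoing-pregnancy visit.** Inputs are from Protocol 6.2.1.1, 6.2.1.3 and 6.2.1.6 (programmed cycles) and 6.2.2.4 and 6.2.2.7 (natural cycles). The LH-surge timing is an assumption.

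| Step | Programmed, shortest | Programmed, longest | Natural, shortest | Natural, longest |
|---|---|---|---|---|
| Start to endometrial check, or to LH surge | 10 | 12 | 0 (assumed) | 14 (assumed) |
| Repeat endometrial check | 0 | 7 | – | – |
| Check to start of progesterone | 0 | 5 | – | – |
| Progesterone start, or LH surge, to transfer | 5 | 5 or 6 | 7 | 7 |
| Transfer to ongoing-pregnancy visit | 56 | 69 | 56 | 69 |
| **Total, days** | **71** | **98 or 99** | **63** | **90** |
| **Weeks** | **10.1** | **14.0 or 14.1** | **9.0** | **12.9** |

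The choice of 5 or 6 days depends on whether the day progesterone starts is counted as the first day. Without a repeat check the longest programmed lag is 12 + 5 + 6 + 69 = 92 days (13.1 weeks).

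**What the literal reading removes.** A programmed cycle counts only if it is initiated early enough for the scan to fall inside the window. That rules out cycles begun in roughly the last 10 to 14 weeks.

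- *Women whose 12 months ended before the hold.* The hold followed 19 March 2020 (SAP 9.3.2), so these are women randomized before about 19 March 2019. The planned first visit was Q3 2018 (Protocol 3.1.3), so the plan allows for such women. For them 12 study months equals 12 calendar months. Analysis 2 should match the primary exactly, yet the literal rule applies the full cut.
- *Women whose window spans the whole hold.* Their clock runs longer by the length of the hold, so the cut relative to the primary is lag minus hold. The documents do not give the hold's length. For assumed holds:

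| Hold (assumed) | Cut relative to the primary, programmed cycles |
|---|---|
| 4 weeks | 10.1 − 4 to 14.1 − 4 = about 6 to 10 weeks |
| 8 weeks | about 2 to 6 weeks |
| 12 weeks | none to about 2 weeks |
| 16 weeks | none |

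**Live birth.** If the observation wording carried over to SAP 11.1.1, the cut would be far larger. The protocol dates gestation from transfer plus 19 days (Protocol 8.5.1, stillbirth footnote), so 37 weeks is 259 − 19 = 240 days after transfer. The shortest programmed path to transfer is 10 + 5 = 15 days. A birth at 37 weeks or later then comes at least 255 days after initiation, so no cycle begun after day 365 − 255 = 110 could produce one inside 365 days.

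**The case against.** The best defence is that the SAP already supplies the right reading. It coins 12 study months as an initiation period, the disputed sentence says it repeats the primary methodology, and nothing says that a pregnancy confirmed after the window from a cycle begun inside it is excluded. The literal reading also defeats the purpose of the analysis and gives an absurd result for live birth. This largely stands: initiation was probably intended.

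It does not settle the text. For analysis 1 the SAP spells out the repeated methodology as the analysis set, the inference method and the imputation method. The counting window is not on that list, and analysis 1 changes it in its own qualifying clause. In analysis 2 the qualifying clause again carries the counting rule, and there it refers to observation.

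A reader might infer more than the documents support:

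- *That every woman loses her last 10 to 14 weeks.* Women with an earlier ongoing pregnancy, with no blastocysts left or with no late cycle lose nothing. For women whose window spans the hold, the longer clock offsets some or all of the cut.
- *That the FE 999049 rate falls by a known amount.* The documents do not say what share of pregnancies come from late cycles. Protocol 3.5.2 says most returning women undergo two to three cryopreserved cycles and that six months would be enough if all cycles were natural, which suggests that late cycles may be few.
- *That the trial's conclusion is at risk.* This is one of three supportive COVID-19 analyses. With placebo at 3%, the SAP 9.3.1 rule keeps at least 99% power with a true FE 999049 rate of 22%, and 96 to 99% at 20%.

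**Conclusion.** The mismatch is real and minor. The wording allows two readings that give different results, and the SAP does not choose between them. The literal one would omit ongoing pregnancies from programmed cycles begun in about the last 10 to 14 weeks of the study-month window, and from natural cycles begun in about the last 9 to 13 weeks under the LH-surge assumption. It changes the outcome only for a woman whose first ongoing pregnancy comes from such a cycle. The clearest harm is among women who finished before the hold, where any gap from the primary would come from the counting rule alone. The effect on the estimated rate cannot be sized from the documents, and its net direction depends on how many pregnancies the extension recovers. The primary test, alpha and power do not depend on this sentence.

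**What to change.** In SAP 9.3.2, replace the qualifying clause of analysis 2 with: *but using ongoing pregnancies from the fresh cycle and from cryopreserved cycles initiated within 12 study months, whenever the 8-9 week assessment took place.* In SAP 11.1.1, state the matching rule for the live-birth repeat: births from cycles initiated within the same window, whenever delivery occurs. It would also help to state how active study days are counted around the hold, so that the window can be derived without further interpretation.

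The cost is one phrase in 9.3.2, a sentence in 11.1.1 and the matching derivation. No new data are needed, and the primary analysis does not change.

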9.4 Secondary Efficacy Endpoints

Secondary efficacy endpoints will be analyzed based on the mITT analysis set. As specified below, for selected endpoints, analyses will be repeated on the PP analysis set.

For secondary efficacy endpoints that are collected in the cryopreserved cycles, additional summaries will be tabulated by whether or not the cycle occurred before, concurrently during, or after the conclusion of the COVID-19 pandemic trial hold. It is anticipated that the number of cryopreserved cycles that are concurrent with or initiated after the COVID-19 pandemic trial hold will be small therefore only descriptive statistics, and not inferential statistics, will be applied to the three groupings.

Ferring Pharmaceuticals

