6.2.1.1 Cycle Initiation / Preparation of the Endometrium

Start of Estradiol

Any programmed cryopreserved cycle is to be initiated within 3 days of start of menses when subjects starts preparation of the endometrium with estradiol.

At that time, the following must be performed:

- Physical examination
- Gynecological examination
- Urine pregnancy test must be negative
- Vital signs (systolic blood pressure, diastolic blood pressure, pulse)
- Dispensing of estradiol
 The subject will start endometrial preparation with estradiol 2 mg TID or 3 mg BID (or 3 mg TID, if a daily dose of 6 mg has been shown to be insufficient in a previous cycle)
- Recording of use of any concomitant medication
- Recording of adverse events

Evaluation of Endometrium

After 10-12 days of estradiol treatment the following must be performed:

- Transvaginal ultrasound of uterus to measure endometrial thickness
 Based on the results of the endometrial evaluation one of the following will take place:
 - If endometrial thickness is ≥8 mm, the estradiol dose will be continued and daily intramuscular (IM) injections of 50 mg progesterone will be initiated within 5 days
 - If endometrial thickness is <8 mm, the estradiol dose will be continued and endometrial thickness measurement repeated within 7 days
- Dispensing of IM progesterone, if applicable
- Dispensing of estradiol
- Drug accountability of estradiol
- Recording of use of any concomitant medication
- Recording of adverse events

Date: 25 Apr 2018 E-Study Protocol-22377; Ver. 1.0 Supersedes: None

Page 85 of 159

For subjects with an endometrial thickness ≥ 8 mm, the next visit is the transfer visit on the 6^{th} day from start of progesterone treatment (section 6.2.1.3).

For subjects with endometrial thickness <8 mm, the endometrial thickness measurement will be repeated within 7 days. If the criterion of endometrial thickness ≥8 mm is reached at the repeated measurement, daily IM injections of 50 mg progesterone will be initiated within 5 days.

Subjects who fail to achieve adequate endometrial thickness will discontinue estradiol and will be administered 100 mg IM progesterone to induce withdrawal bleeding. In subsequent cryopreserved cycles, blastocyst transfer can take place regardless of endometrial thickness at the investigator's discretion.

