Recruitment to the trial has been completed and all fresh cycles have been completed up to the ongoing pregnancy visit. The current activities are cryopreserved cycles initiated within 12 months from the start of controlled ovarian stimulation as well as pregnancy follow-up to birth, 4 weeks and 1 year after birth in the fresh and cryopreserved cycles.

Ferring is issuing guidance for continued trial conduct and management of subjects included in the trial. The table below provides guidance for how to manage the subjects according to stage in the trial.

Continued trial conduct for management of subjects included in the trial

- Cryopreserved cycles:
 - Cycles not yet initiated: do not initiate until this COVID-19 related temporary deferral of cryopreserved cycles has been lifted
 - Cycles already initiated and where transfer has not occurred: continue per protocol and document any deviations
 - Cycles where transfer has occurred: continue per protocol and document any deviations
 - Note: timelines for cryopreserved cycles will be extended by the approximate duration
 of the temporary deferral of cryopreserved cycles required by this change to the
 protocol
- Pregnancy follow-up: continue per protocol and document any deviations

In case subjects are prevented from attending scheduled visits, the investigator (or designee) will attempt to contact the subject by phone or other ways to inquire about potential adverse events and changes to concomitant medication.

Page 4 of 4

IMPLICATIONS OF CHANGE:

The implications of these changes to the protocol are summarized below. The actions are considered urgent safety measures due to COVID-19 required to protect subjects against immediate hazard to their health and safety and are therefore implemented immediately.

- Trial sites, regulatory authorities and independent research boards will be informed.
- Subjects will be verbally informed by the investigator of potential changes to the course of
 action, as applicable for the individual subject. This will be documented in the subject's
 medical records.
- Protocol deviations (including deviations to the aspects described in this 'change to
 protocol') should be avoided whenever possible except where necessary to eliminate an
 immediate hazard to the subject. If deviations occur they will be documented as per
 standard practice, with additional specification whether they were related to the COVID-19
 situation.

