For subjects who started at least one cryopreserved cycle, as indicated by initiating estradiol for programmed cycles or by initiating LH surge monitoring for natural cycles, the subject disposition with respect to blastocyst thawing, blastocyst transfer and cycle completion will be summarized by type of cryopreserved cycle (programmed and natural) and overall in sequential order. For each cryopreserved cycle, the denominator is the total number of subjects who started the respective cycle. The transfer completion/cancellation and the cycle completion/discontinuation statuses will be summarized including the reasons for cycle cancellation and for not completing the cycle respectively.

Finally, the following summary statistics will be presented: the number and percentages of subjects who underwent stimulation with IMP, who underwent transfer in the fresh cycle, who underwent transfer in at least one cryopreserved cycle (total and separate for programmed and natural cryopreserved cycles), as well as the total number of cryopreserved cycles and the total numbers of programmed and natural cryopreserved cycles respectively. The denominator will be based on the ITT population.

Subject disposition with respect to analysis sets will be listed for all randomized subjects including information on cycle completion status by cycle, whether the cycle was completed before, coincided with, or was initiated after the COVID-19 pandemic trial hold period, and reason for cycle termination, sorted by treatment group, subject ID and cycle in overall sequential order. Subjects who did not complete the COS with IMP and who had a fresh/cryopreserved transfer cancellation will also have the early termination and transfer cancellation information listed separately.

5 **Protocol Deviations**

The rating of protocol deviations as 'minor' and 'major', as well as the criteria for major protocol deviations with the implication of exclusions from the per-protocol (PP) analysis set will be decided by the medical officer, medical monitor and statistician on the basis of a blinded review of data before declaration of clean file and lock of database.

The list of major protocol deviations will be detailed and documented in the clean file document prior to database release. Major protocol deviations will be summarized and listed by subject.

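### SAP 9.4 groups cryopreserved cycles by overlap with the COVID-19 hold, so membership depends on outcome and per-cycle pregnancy rates in the concurrent group are biased upward in expectation

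*SAP*

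**What the plan says.** SAP 9.4 adds summaries of the cryopreserved-cycle secondary endpoints "tabulated by whether or not the cycle occurred before, concurrently during, or after the conclusion of the COVID-19 pandemic trial hold". It gives no explicit rule for assigning a cycle to a group. It expects the number of "cryopreserved cycles that are concurrent with or initiated after the COVID-19 pandemic trial hold will be small" and limits the three groups to descriptive statistics.

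The clearest wording of the three groups is in SAP Section 4 (Subject Disposition), where a listing shows "whether the cycle was completed before, coincided with, or was initiated after the COVID-19 pandemic trial hold period".

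Protocol Amendment 01 (Summary of Changes #01) sets what could happen during the hold. For new cycles: "Cycles not yet initiated: do not initiate until this COVID-19 related temporary deferral of cryopreserved cycles has been lifted". Cycles already started could go on: "Cycles where transfer has occurred: continue per protocol and document any deviations". On timing, SAP 9.3.2 says that "the trial hold began subsequent to the issuing of Protocol Amendment 01 on 19 March 2020". Neither document gives the length of the hold.

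SAP 9.4.1 calculates pregnancy rates on two denominators: all subjects in the treatment group, and subjects who started the respective cycle. This point concerns the second.

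**The concern.** No cycle could start during the hold, so a cycle can be concurrent with it only by being open when it began. How long a cycle stays open depends on how it turns out. A negative test closes it about two weeks after transfer, while an ongoing pregnancy keeps it open until the scan at 8-9 weeks. Cycles open on a fixed calendar date are therefore a length-biased sample in which successes are over-represented, and the before group, if defined by completion, loses the corresponding successes.

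What is at stake is how these tables are read. A reader comparing the three columns would expect similar rates if the pandemic did nothing. The grouping instead produces a gap in expectation with no pandemic effect, and that gap could hide a real fall during the hold.

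**Working it through.** The plan states no figure for this grouping, so there is none to reproduce. The check builds cycle lengths from the protocol's windows and applies the length-bias formula.

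**Step 1. Who is in the concurrent group.** Grouping by initiation date would leave the concurrent group empty apart from deviations, because Amendment 01 says "do not initiate until this COVID-19 related temporary deferral of cryopreserved cycles has been lifted". SAP 9.4 nevertheless expects some concurrent cycles. The reading that fits SAP 9.4, SAP Section 4 and the amendment together is cycles open at hold start, whatever the hold's length.

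**Step 2. Cycle length by outcome** (programmed cycles without re-evaluation; Protocol 6.2.1.1 to 6.2.1.7).
- Initiation to endometrial evaluation: 10-12 days ("After 10-12 days of estradiol treatment the following must be performed").
- Evaluation to progesterone: 0-5 days.
- Progesterone to transfer on the 6th day: 5 days.
- Initiation to transfer: 10+0+5 = 15 to 12+5+5 = 22 days.

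The cycle ends at the last scheduled visit:
- Negative test, 10-14 days after transfer: 25-36 days (midpoint 30.5).
- No vital pregnancy, 35-48 days after transfer: 50-70 days (midpoint 60).
- Ongoing pregnancy, 56-69 days after transfer: 71-91 days (midpoint 81).

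Midpoint ratios are 81/30.5 = 2.66 for success against a negative test, and 81/60 = 1.35 for success against no vital pregnancy.

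**Step 3. Mean length of a failed cycle, L0.** The documents do not give the share of failures that end at the 5-6 week visit. Assume 0% to about 32%. Then L0 runs from 30.5 to 0.68×30.5 + 0.32×60 ≈ 40 days. With L1 = 81 for successes, the ratio L1/L0 runs from 2.66 to about 2.0.

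**Step 4. Expected rate in the concurrent group**, with true rate p and steady initiation: p·L1 / (p·L1 + (1−p)·L0).
- p = 32.3% (Protocol 1.1, per initiated cryopreserved cycle in earlier trials), L0 = 30.5: 26.16/(26.16 + 20.65) = 56%.
- p = 32.3%, L0 = 40: 26.16/(26.16 + 27.08) = 49%.
- p = 20%: 16.2/(16.2 + 24.4) = 40% and 16.2/(16.2 + 32.0) = 34%.

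**Step 5. Expected rate in the before group**, with starts assumed uniform over T = 365 to 500 days before the hold: p(T−L1) / [p(T−L1) + (1−p)(T−L0)].
- p = 32.3%, T = 365, L0 = 30.5: 91.7/(91.7 + 226.5) = 29%.
- p = 32.3%, T = 500, L0 = 40: 135.3/(135.3 + 311.4) = 30%.
- p = 20%, the same two corners: 56.8/324.4 = 17.5% and 83.8/451.8 = 18.5%, or about 18%.

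**Step 6. Sensitivity to assumptions.**
- Simulation over the visit windows at 32.3%, with 0-30% of failures ending at 5-6 weeks, gives about 30% before and 50-56% concurrent with steady initiation. With declining initiation it gives about 31% and 53-61%. A decline is plausible, since the last randomization was on 17 September 2019.
- Suppose 10% of failures are cancelled at 15 days, 20% end at 5-6 weeks and 5% are losses found at 8-9 weeks. Then L0 = 1.5 + 12 + 4.05 + 19.8 = 37.4 and the concurrent rate is 51%.
- Natural cycles, with the LH surge assumed 3-14 days after initiation, give a success to negative-test ratio of about 2.8 at midpoints.

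**Step 7. The opposing force.** SAP 9.2.2 counts missing pregnancy observations as negative. At a mid-range concurrent rate of 53%, missing 40% of ongoing-pregnancy visits gives 0.53×0.60 = 32%, which cancels the bias. A sizeable loss of information, or a real effect of similar size, could therefore leave the table looking unremarkable.

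**The case against.** The strongest case on the other side has five parts.

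- **Little depends on the table.** It is supplementary, descriptive and expected to be small. The primary test, the live birth test and the three COVID-19 sensitivity analyses in SAP 9.3.2 do not use the grouping. This stands and limits the weight of the point. It does not remove the bias, which is in the point estimates and is not a matter of testing.
- **The definition is inferred.** SAP 9.4 gives no explicit rule, and the sharper wording comes from a disposition listing. It also states no purpose for these summaries; the SAP assigns the assessment of pandemic impact to the primary-endpoint sensitivity analyses. Both are fair. Even so, SAP 9.4's own reference to concurrent cycles, with the ban on new ones, leaves little room for another reading.
- **Not every failed cycle is short.** A reader might infer that successes last more than twice as long as any failure. The protocol's windows do not support that: the ratio is about 1.35 against cycles ending at 5-6 weeks, and losses found at 8-9 weeks last as long as successes.
- **The observed rate need not be higher.** A reader might infer that the concurrent column must show the higher rate. That holds only in expectation. If the expected rate is 51-56%, the chance that the observed rate exceeds 32.3% is about 84-91% with 10 cycles and 95-98% with 20. Missing-as-negative also works against it.
- **The 32.3% is borrowed.** It comes from earlier trials that enrolled women aged 18-40, and this trial enrols women aged 35-42. That is why 20% is shown as well; the direction is the same.

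**Conclusion.** The point holds for the per-started-cycle pregnancy rates in the SAP 9.4 summaries. With no pandemic effect, the expected concurrent rate is about 17 to 24 percentage points above an assumed true rate of 32.3%, and the before rate is 2 to 3 points below it. At an assumed 20% the excess is about 14 to 20 points. These sizes rest on midpoint lengths for programmed cycles, an assumed share of failures ending at 5-6 weeks, and assumed initiation patterns. The direction rests only on the visit schedule and the ban on new cycles.

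A reader might go further and infer that the trial's efficacy conclusion or its COVID-19 sensitivity analyses are distorted. The documents do not support that, because none of those analyses uses this grouping. Nor is the SAP Section 4 listing at fault: it records cycle status and reports no rate, so length bias cannot arise there. This is a correction worth making to a descriptive table.

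**What to change.** Change SAP 9.4 only. For the outcome-rate summaries, group each cryopreserved cycle by its initiation date, which is fixed before the outcome:

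- (a) initiated at least 98 days before the hold began;
- (b) initiated within the 98 days before it began;
- (c) initiated after it was lifted.

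The 98 days is the longest programmed-cycle window: 12 (estradiol) + 7 (re-evaluation) + 5 (to progesterone) + 5 (to transfer) + 69 (to the ongoing-pregnancy visit). It also covers natural cycles under the surge timing assumed above (66-90 days to the ongoing-pregnancy visit). Membership then does not depend on outcome, and the artificial gap is zero in expectation.

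The cost is a sentence in SAP 9.4 and a small programming change, on the same data. The rule needs recorded dates for the start and lifting of the hold, as the present grouping does.

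The downside is that group (b) includes cycles that had already closed. With uniform starts, (98−81)/98 = 17% of successes and (98−40)/98 to (98−30.5)/98 = 59-69% of failures would have closed before the hold. At 32.3% that is roughly 46-52% of the group. Keep the SAP Section 4 listing unchanged, as the factual record of which cycles overlapped the hold.
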